Main Inclusion and Exclusion Criteria	
Inclusion criteria:
 
• Subjects aged 18 years and older, male or female;• Prior diagnosis of COVID-19 (acute symptoms consistent with COVID-19, confirmed by PCR, serologic or rapid antigen test) for the COVID-19 survivors group, or no confirmed or suspected prior history of symptomatic COVID-19 for the control group at the time of enrollment. 
Exclusion criteria:
 
• Pregnancy at the time of the index COVID-19 episode or at the time of the first enrollment in the study; potential participants who become pregnant after the index COVID-19 episode will not be invited to participate until at least 3 months post-delivery. Inability to provide informed consent.• Known history of CVD (defined as HF, MI, coronary revascularization, serious arrhythmia, stroke, greater than moderate valvular heart disease, any cardiomyopathy, or PAD), glomerular disease or polycystic kidney disease prior to enrollment.• End stage kidney disease (ESKD; defined as requiring persistent renal replacement therapy or prior kidney transplant) prior to enrollment• History of chronic kidney disease (CKD) with eGFR <30 mL/min/1.73m² prior to enrollment. In participants without a history of CKD, a measurement of eGFR will not be required for enrollment.
--	---

CONFIDENTIAL

This material is the property of the University of Pennsylvania.

Study procedures	
• The phenotyping protocol will include brief questionnaires, a brief ultrasound examination, arterial tonometry, measurements of endothelial function, a 6-minute walk test, pulmonary function tests, Short Physical Performance Battery, impedance cardiography, blood, urine and breath condensate collection and 24-hour blood pressure monitoring. A subset of participants will be asked to complete a cardiopulmonary supine bike exercise test. All tests except for VO2 testing will be repeated at approximately 18-month intervals for a total of 3 tests

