3.1 General Design

This is a prospective cohort study of 200 COVID-19 survivors and 80 control subjects without a known history of symptomatic COVID-19. Among survivors, we will prioritize subjects who had their index infection within the last 12 months. However, will allow for index infections acquired outside of this timeframe to facilitate enrollment. We will collect detailed measures of cardiovascular, pulmonary, renal structure and function, along with various other measures, as follows:

- (1) Endothelial function: flow-mediated brachial artery dilation and venous endothelial cell harvesting for molecular analyses.

CONFIDENTIAL

- (2) Arterial stiffness: carotid-femoral pulse wave velocity and carotid artery stiffness measurements.
- (3) Central pulse pressure and measurements of stroke volume and arterial compliance by impedance cardiography.
- (4) Subclinical atherosclerosis: carotid intima-media thickness and ankle-brachial index.
- (5) Pulmonary Function tests
- (6) Microvascular function: forearm ischemic vasodilation, and microvascular imaging with sublingual *in vivo* microscopy
- (7) A brief focused ultrasound test (liver, kidney, skeletal muscle, cardiac and carotid ultrasound), performed by a trained research team member.
- (8) Biosample collection (blood, urine and breath condensate)
- (9) A 6-minute walk test
- (10) A Kansas City Cardiomyopathy Questionnaire (KCCQ)
- (11) A subset of questions from the PROMIS Questionnaire to evaluate mental and physical function
- (12) A long COVID symptom Questionnaire
- (13) EQ-5D-5L Questionnaire
- (14) Social determinants of health questionnaire
- (15) Short Physical Performance Battery (SPPB)
- (16) In a subset of participants, we will also perform supine bicycle exercise tests to assess aerobic capacity (i.e., peak oxygen consumption, VO₂).

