3.3 Exclusion Criteria

- Pregnant women;
- Inability to provide informed consent.
- History of CVD (defined as HF, MI, coronary revascularization, serious arrhythmia, stroke, greater than moderate valvular disease, any cardiomyopathy, or PAD), glomerular disease or polycystic kidney disease prior to enrollment.

CONFIDENTIAL

- End stage kidney disease (ESKD; defined as requiring persistent renal replacement therapy or prior kidney transplant) prior to enrollment
- History of chronic kidney disease (CKD) with eGFR <30 mL/min/1.73m² prior to enrollment. In participants without a history of CKD, a measurement of eGFR will not be required for enrollment.

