The endpoint of MACE will be evaluated as a time-to-event endpoint from the date of discharge from the index hospitalization for COVID-19 and from the date of the first study visit, accordingly. We will examine the associations of severity of hospitalization, baseline covariates, and post-discharge cardiac and extra-cardiac phenotypes with this failure-time event using Kaplan-Meier curves and Cox proportional hazards regression ¹²⁵. We will use the multivariable Cox model to

CONFIDENTIAL

estimate the effects of the primary exposure adjusting for baseline covariates. We will use time by covariate interaction terms and examine residual plots to assess the adequacy of model fit ¹²⁶. If the proportional hazards assumption is violated, a time by predictor interaction term will be added to the model to allow for changes in the HR over time. Secondary analyses will evaluate death prior to the event as a competing risk, including incorporation of the composite outcome with the cumulative incidence function ^{127,128}. We will assess for effect modification by sex and race due to sex- and race-related differences in COVID-19 outcomes ¹¹⁸⁻¹²⁰ and risk of MACE ^{121,129}.

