4.2 Power calculations

We will enroll 200 COVID-19 survivors following recovery from their hospitalization and 80 controls. For analyses of trajectory of vascular and kidney health, accounting for multiplicity across multiple outcome parameters at an alpha at 0.0025, ¹³⁰ we will have >80% power to observe, for example, a mean difference in slope of PWV of 0.8 m/s and eGFR of 4 mL/min/1.73m² per 18-month visit interval across COVID-19 survivors and non-COVID-19 controls, assuming intraclass correlation coefficient of 0.1 and 20% loss to follow-up.¹³¹ For determining the association of hospitalization severity with risk of MACE, the most conservative endpoint in the study, we assumed a cumulative event rate of 5% over 5 years of follow-up ^{6,7}, accounting for our exclusion of individuals with prior CVD. Assuming a retention rate of 80%, we will have 90% power at an alpha of 0.05 to detect a regression coefficient of 0.9 in the Cox model ^{132,133}. In analyses evaluating for sub-phenotypes and risk factors for MACE, using a conservative Bonferroni approach to account for multiplicity across several risk factors ¹³⁰, we will have over 90% power at an alpha of 0.005 to detect a regression coefficient of 0.9 for every standard deviation difference in parameter. Power calculations were performed using PASS16 ¹³⁴.

5 Study Administration, Data Handling, and Record Keeping

All information obtained as part of protocol will be maintained in locked research files. Electronic data will be stored in a password secured database (REDCap). This database will be available only with secure high-level password protection to safeguard the privacy of the participants. Any source documents for each patient involved in the protocol, other than the patient's electronic medical chart, will be maintained in a centralized, secured location.

Data collected will contain protected health information (PHI) including name, date of birth, and medical record number. Information about study subjects will be kept confidential and managed according to the requirements of the Health Insurance Portability and Accountability Act of 1996 (HIPAA). Research data will be stored in a centralized, secure location (locked cabinets in the PI's research space).

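### MACE may be timed from discharge with no rule for entry at the first visit, so a nearly event-free pre-enrolment gap would count as time at risk and early risk would read low

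*Combined protocol and SAP*

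**What the plan says.** Section 4.1 evaluates MACE as a time-to-event endpoint "from the date of discharge from the index hospitalization for COVID-19 and from the date of the first study visit, accordingly". The next sentence examines "associations of severity of hospitalization, baseline covariates, and post-discharge cardiac and extra-cardiac phenotypes with this failure-time event using Kaplan-Meier curves" and Cox regression, so severity, covariates and phenotypes share one endpoint and none is given its own origin. Competing-risk analyses follow, "including incorporation of the composite outcome with the cumulative incidence function". Delayed entry, left truncation and landmarks are not mentioned anywhere.

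Eligibility is judged at enrolment. The synopsis excludes "Known history of CVD (defined as HF, MI, coronary revascularization, serious arrhythmia, stroke, greater than moderate valvular heart disease", among other conditions. Section 3.3 gives a near-identical list, ending "any cardiomyopathy, or PAD), glomerular disease or polycystic kidney disease prior to enrollment". Section 3.1 prioritises index infections in the last 12 months but "will allow for index infections acquired outside of this timeframe to facilitate enrollment", so the gap has no upper limit.

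The power section addresses severity first: "For determining the association of hospitalization severity with risk of MACE, the most conservative endpoint in the study". There, "we assumed a cumulative event rate of 5% over 5 years of follow-up", with 80% retention and a Cox coefficient of 0.9.

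**The concern.** A survivor who had a myocardial infarction, stroke or heart failure after discharge but before the first visit is ineligible, and one who died cannot enrol. Everyone in the cohort has therefore come through the gap almost free of MACE by selection. If the clock starts at discharge and everyone is counted at risk from then, the gap adds person-time in which almost no qualifying event could be seen. This is immortal time, and it pulls absolute risk curves down.

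The distortion is greatest early. That is when Section 1 (A2) reports raised risk after pneumonia: a hazard ratio of 2.10 from 91 days to one year and 1.89 in the second year. Section 1 (A7) gives unknown incidence as a reason for the study. A curve that is flat at first because of enrolment rules could be taken as evidence of low early risk after COVID-19.

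**Working it through.** **Inputs from the documents.** 200 survivors, 80% retention, 5% risk over 5 years and coefficient 0.9 (Section 4.2). Expected events: 200 × 0.80 × 0.05 = 8 among 160 people. Constant hazard: λ = −ln(0.95)/5 = 0.01026 per year, which returns the plan's figure: 1 − exp(−5λ) = 5.0%.

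**Assumptions.** The documents give no gap length. I take the gap G as uniform from 0 to 2m, with mean m of 3, 6 or 12 months; the last puts half of survivors outside the prioritised 12 months. Entry is otherwise unrelated to risk, anyone with an event in the gap is not enrolled, and everyone is counted at risk from discharge.

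**Step 1: risk as it would read.** By time t the curve shows the average over G of 1 − exp(−λ·max(t − G, 0)), roughly λ times the mean time actually at risk.

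- One year: mean time at risk is 0.75, 0.50 or 0.25 years. For example, 0.01026 × 0.25 = 0.26%.
- Five years: mean time at risk is 4.75, 4.5 or 4.0 years. For example, 1 − exp(−0.01026 × 4.0) = 4.0%.

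| Horizon | True | m = 3 months | m = 6 months | m = 12 months |
|---|---|---|---|---|
| 1 year | 1.02% | 0.77% | 0.51% | 0.26% |
| 2 years | 2.0% | 1.8% | 1.5% | 1.0% |
| 5 years | 5.0% | 4.8% | 4.5% | 4.0% |

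One-year risk is understated by a quarter, a half or three quarters, which is about 0.4, 0.8 or 1.2 events among 160. Now suppose the hazard is front-loaded, with relative hazards of 2.10 in year one, 1.89 in year two, and 1.0 or 1.89 after that (the later values are assumed). Five-year risk then reads 4.6–4.7%, 4.3–4.5% or 3.6–4.0%.

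**Step 2: sampling error.** The exact 95% interval for 8/160 is 2.2% to 9.6%. Every five-year value above lies inside it.

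**Step 3: severity hazard ratio.** Take two equal halves, milder and more severe, with true HR exp(0.9) = 2.46. With few events, the Cox estimate without delayed entry is close to 2.46 × (mean time at risk, severe)/(mean time at risk, milder).

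- Equal gaps: the ratio is 1, so there is no bias.
- 3 months (milder) v 12 months (severe), five-year cut from discharge: 2.46 × 4.0/4.75 = 2.07; numerical solution 2.06.
- Same gaps, three-year cut: 2.46 × 2.0/2.75 = 1.79; numerical solution 1.78.
- Gaps reversed: 2.93 (five-year) and 3.39 (three-year).

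Size against imprecision: 160 people generate 160 × 0.01026 = 1.64 events per year of mean time at risk.

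- Five-year cut: 1.64 × (4.75 + 2.46 × 4.0)/3.46 ≈ 7 events. SE = 2/√7 = 0.76; shift ln(2.46/2.06) = 0.18, or about 0.23 SE.
- Three-year cut: 1.64 × (2.75 + 2.46 × 2.0)/3.46 ≈ 3.6 events. SE = 2/√3.6 = 1.05; shift ln(2.46/1.78) = 0.32, or about 0.31 SE.

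**Step 4: who has a discharge date.** Section 3.2 does not require hospitalisation, objective 2 in Section 2 speaks of severity of COVID-19, and Section 3.6.1 ranks all subjects and scores those never admitted. Sections 4.1 and 4.2 speak of severity of hospitalisation, and Section 4.2 describes the survivors as recovered from one. These texts point to different analysis sets, and never-hospitalised survivors have no discharge date. If 75% or 50% were hospitalised (assumed, same 5% risk), a hospitalised-only model would have 6 or 4 expected events instead of 8. The per-SD standard error would rise from 1/√8 = 0.35 to 0.41 or 0.50.

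**The case against.** The strongest reply is that the plan does not commit to the faulty analysis. The word *accordingly* suggests a mapping, probably discharge for severity and first visit for phenotypes. Delayed entry is not ruled out, and the survival reference cited is a textbook on censored and truncated data. Kaplan-Meier is planned to examine associations, and no one-year or five-year risk is a named target. With about 8 events, the origin is unlikely to change any conclusion.

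Much of this stands. The phenotype analyses are probably unaffected, the consequence is modest next to imprecision, and all gap lengths are assumed. But the likely mapping puts the severity analysis on the origin that needs an entry rule, and a textbook citation does not supply one. Applied as written, the discharge origin gives curves that are wrong in a known direction.

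Three stronger readings go beyond the documents:

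- *That the severity hazard ratio is biased.* This needs the gap to differ by severity, which is neither stated nor excluded.
- *That the gap is strictly event-free.* TIA counts as MACE in Table 2 but is not a named exclusion, the synopsis excludes only known disease, and the record review could pick up a TIA in the gap.
- *That every MACE analysis must start at the first visit.* That would drop a planned post-discharge time scale; it is a trade-off, not a correction.

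**Conclusion.** The concern holds for analyses timed from discharge, not for those timed from the first visit. Kaplan-Meier and cumulative incidence curves would read low. The relative error is large in the first year (25% to 75% under the assumed gaps) and small at five years (0.24 to 0.98 points, inside sampling error). These figures rest on the plan's 5% risk, a mainly constant hazard and gap lengths that the documents do not give. Any effect on the severity hazard ratio is conditional. Its size depends on the assumed imbalance and on the follow-up horizon, and it came to about 0.3 standard errors or less in the 3 v 12 month cases worked through in step 3. Confidence is high on the missing rule and the direction of the error, and low on its exact size. Whether never-hospitalised survivors belong in the severity model is a secondary inconsistency; a reader might infer either answer, and the text settles neither.

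**What to change.** In Section 4.1:

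1. Name the first study visit as time zero for the phenotype analyses.
2. Where discharge is kept as the time scale, enter each participant into the risk set at the first visit (left truncation) in Kaplan-Meier, Cox and cumulative incidence alike.
3. State that results are conditional on being alive and free of known cardiovascular disease at enrolment.
4. Reconcile Sections 2, 3.2 and 3.6.1 with Sections 4.1 and 4.2 on whether never-hospitalised survivors are in the severity model. If they are, use one common origin for everyone in it.

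**Cost.** Items 1 and 3 need only wording, and item 4 a decision and wording. Item 2 needs discharge dates from the planned record review and left-truncated estimators, including one for cumulative incidence, which takes some programming. The statistical price is very imprecise early risk: about 1.2, 0.8 or 0.4 events would be expected in the first year after discharge among 160 people, for mean gaps of 3, 6 or 12 months. Using the first visit throughout would be simpler, but risk from discharge would then not be estimated and survivors at different times since infection would be pooled. The choice should be written down before outcome data are analysed.

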4.2 Power calculations

We will enroll 200 COVID-19 survivors following recovery from their hospitalization and 80 controls. For analyses of trajectory of vascular and kidney health, accounting for multiplicity across multiple outcome parameters at an alpha at 0.0025, ¹³⁰ we will have >80% power to observe, for example, a mean difference in slope of PWV of 0.8 m/s and eGFR of 4 mL/min/1.73m² per 18-month visit interval across COVID-19 survivors and non-COVID-19 controls, assuming intraclass correlation coefficient of 0.1 and 20% loss to follow-up.¹³¹ For determining the association of hospitalization severity with risk of MACE, the most conservative endpoint in the study, we assumed a cumulative event rate of 5% over 5 years of follow-up ^{6,7}, accounting for our exclusion of individuals with prior CVD. Assuming a retention rate of 80%, we will have 90% power at an alpha of 0.05 to detect a regression coefficient of 0.9 in the Cox model ^{132,133}. In analyses evaluating for sub-phenotypes and risk factors for MACE, using a conservative Bonferroni approach to account for multiplicity across several risk factors ¹³⁰, we will have over 90% power at an alpha of 0.005 to detect a regression coefficient of 0.9 for every standard deviation difference in parameter. Power calculations were performed using PASS16 ¹³⁴.

5 Study Administration, Data Handling, and Record Keeping

All information obtained as part of protocol will be maintained in locked research files. Electronic data will be stored in a password secured database (REDCap). This database will be available only with secure high-level password protection to safeguard the privacy of the participants. Any source documents for each patient involved in the protocol, other than the patient's electronic medical chart, will be maintained in a centralized, secured location.

Data collected will contain protected health information (PHI) including name, date of birth, and medical record number. Information about study subjects will be kept confidential and managed according to the requirements of the Health Insurance Portability and Accountability Act of 1996 (HIPAA). Research data will be stored in a centralized, secure location (locked cabinets in the PI's research space).

Participant data, blood, and urine samples will be stored for future use. These stored elements will be used only for research purposes. A randomly assigned number rather than name will identify all collected samples and data. PHI will be treated with strict confidentiality and stored in a secured, limited access area. A secure database of patient information will be maintained. PHI will not be disclosed or shared with any parties outside of the research team unless required by law or by regulatory processes at Penn (such as audits).

6 Study Monitoring, Auditing, and Inspecting

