4.1 Data analysis plan

To characterize cardiac and extracardiac phenotypes in COVID-19 survivors, we will use latent class analysis with finite mixture modeling to classify individuals into mutually exclusive and exhaustive subgroups, maximizing within-group similarities and between-group differences on the basis of baseline covariates ¹⁰⁹⁻¹¹². Latent class models will be compared across successive numbers of subgroups and the optimal number of groups will be determined using the parametric bootstrap likelihood ratio test, Akaike's Information Criterion, Bayesian Information Criterion, and sample-size adjusted BIC ^{113,114}. We will use other clustering methods for corroboration of our identified phenotypes, including Gaussian mixture models via the expectation–maximization algorithm ⁷⁹, and consensus clustering ¹¹⁵ to evaluate the stability of the discovered clusters. Descriptive statistics will compare patients across phenotypes using Student's t-test, Wilcoxon rank sum, or Chi-square test, as appropriate. We will then assess for differences in quality of life and functional status across phenotypes using multinomial logistic regression. We will separately analyze the trajectory of each of the quantitative measures of vascular health and kidney function using mixed effects growth curve models.¹¹⁶ Where necessary, we will supplement these analyses with marginal models estimated by generalized estimating equations.¹¹⁷ We will assess for varying length of follow-up among subgroups to evaluate for any potential bias this may introduce. We will assess for effect modification by sex and race due to potentially important differences in COVID-19 outcomes¹¹⁸⁻¹²⁰ and trajectory of vascular and kidney health.^{121,122} We will also use methods that classify participants according to their vascular and kidney health trajectories, using each individual parameter and extended to multiple parameters. We will use the latent class mixed effects model^{123,124} to analyze trajectories of vascular and kidney health within our study population. The latent class mixed effects model introduces an additional variable to represent class membership, which can be modeled through a multinomial logistic regression.

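### The over-90% power in section 4.2 for sub-phenotypes and MACE does not follow from the plan's expected events, and a per-SD figure does not carry over to latent classes

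*Combined protocol and SAP*

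**What the plan says.** Section 4.2 of the combined protocol and SAP makes two power statements about MACE.

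- For severity of the index episode: "we assumed a cumulative event rate of 5% over 5 years of follow-up". With 80% retention, "we will have 90% power at an alpha of 0.05 to detect a regression coefficient of 0.9 in the Cox model".
- For the wider set of predictors: "In analyses evaluating for sub-phenotypes and risk factors for MACE, using a conservative Bonferroni approach", the plan claims "we will have over 90% power at an alpha of 0.005 to detect a regression coefficient of 0.9 for every standard deviation difference in parameter". This sentence gives no event rate or retention of its own.

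Section 4.1 starts its phenotyping analysis with a categorical method: "we will use latent class analysis with finite mixture modeling to classify individuals into mutually exclusive and exhaustive subgroups". The number of classes is left to fit criteria, and no class sizes are given. The same section then relates cardiac and extracardiac phenotypes to MACE by Kaplan-Meier curves and Cox regression. No power is stated for a contrast between classes.

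**The concern.** There are two separate problems. First, tightening alpha from 0.05 to 0.005 while keeping the coefficient at 0.9 should lower power. Yet the second statement claims at least as much power as the first, and few events are expected. Second, one figure on a per-SD scale is offered for both risk factors and sub-phenotypes. A predictor scaled to its own SD has variance 1; an indicator of class membership does not.

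The relation of phenotypes to prognosis is part of the primary objective and is specific objective 1(d) in section 2. A reader who relies on the stated power could take a non-significant class or risk-factor result as evidence against a hazard ratio of about 2.5, when the comparison could easily miss one.

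**Working it through.** **Inputs from section 4.2.** 200 survivors and 80 controls; 5% cumulative events over 5 years; 80% retention; coefficient 0.9, so HR = exp(0.9) = 2.46; alpha 0.005.

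**Assumptions.** The 5% and 80% in the severity statement also apply to the next sentence, and the 5% applies to controls when they are counted. Tests are two-sided unless noted. There is no correlation with other covariates.

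**Expected events, D**
- Survivors, 80% retained: 200 × 0.8 × 0.05 = 8
- All participants, 80% retained: 280 × 0.8 × 0.05 = 11.2
- All participants, no loss: 280 × 0.05 = 14

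**Step 1: the plan's own figure, continuous predictor per SD.** Power = Φ(0.9 × √D − z), with z = 2.807 for two-sided 0.005.

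| D | 0.9√D | Power, two-sided | Power, one-sided (z = 2.576) |
|---|---|---|---|
| 8 | 2.546 | 39.7% | 48.8% |
| 11.2 | 3.012 | 58.1% | 66.9% |
| 14 | 3.367 | 71.2% | 78.6% |

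Events needed for 90%: (2.807 + 1.282)² / 0.81 = 20.6 two-sided, or 18.4 one-sided. To reach 20.6 events, the 5% would have to be 12.9% (20.6/160), 9.2% (20.6/224) or 7.4% (20.6/280). The stated figure is not reproduced under any of these variants. A simulated score test (8,000 runs each, two-sided) gave 38% with 160 participants and 54% with 224.

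The companion claim of 90% at alpha 0.05 can be approached: 92.0% with 14 events two-sided, or 91.4% with 11.2 events one-sided. With 8 events it is 72.1% two-sided or 81.6% one-sided. The event count that gives exactly 90% at 0.05 (13.0 two-sided, 10.6 one-sided) gives only 67% or 64% at 0.005. The two statements therefore conflict if they share events and predictor scale.

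**Step 2: a coefficient of 0.9 between two latent classes.** With share p in one class, the indicator's variance is p(1−p), at most 0.25. Power = Φ(0.9 × √(D·p(1−p)) − 2.807). For example, with D = 8 and p = 0.5: 0.9 × √2 = 1.273, and Φ(−1.534) = 6.3%.

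| Class share (assumed) | D = 8 | D = 11.2 | D = 14 | Events for 90% |
|---|---|---|---|---|
| 50% | 6.3% | 9.7% | 13.1% | 83 |
| 25% | 4.4% | 6.6% | 8.9% | about 110 |
| 10% | 2.1% | 2.9% | 3.6% | 230 |

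The highest one-sided value is 18.6% (50:50, 14 events). If the 20.6 events needed in Step 1 are granted, two-sided power at 50:50 is still Φ(0.9 × √(20.6 × 0.25) − 2.807) = 22%.

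The formula is rough here. In simulation with 160 and 224 participants, a 50:50 split gave about 3% and 5–6%. A 20% high-risk class gave 11% and 15%, and an 80% high-risk class about 0%.

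**Step 3: 0.9 read per SD of the class indicator.** The between-class coefficient is then 0.9/√(p(1−p)). At 50:50 it is 1.80 (HR 6.0); at 25:75 it is 2.08 (HR 8.0). The power is that of Step 1, 40–71%.

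**Step 4: detectable hazard ratio between two equal classes, 90% power at two-sided 0.005.** exp(4.089/√(0.25·D)): with D = 8, exp(2.89) = 18; with D = 14, exp(2.19) = 8.9.

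**The case against.** The strongest reply is that the sentence was never meant for latent classes. It speaks of a parameter and of several risk factors. The plan also uses the word phenotype for single quantitative measures: Table 1 has a column of phenotypes of interest that lists liver stiffness, muscle thickness and intima-media thickness, and section 3.6.1 calls the 6-minute walk test a phenotype. Section 4.1 does not say that the phenotypes in the Cox analysis are only the latent classes. This stands. A reader might infer that all the plan's phenotypes are mutually exclusive classes, and the documents do not support that. The difficulty is that section 4.2 names sub-phenotypes alongside risk factors without saying which kind it means, and section 4.1 does build classes.

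It is also fair that the plan nowhere claims to detect 0.9 between classes, so Step 2 tests an effect of the reviewer's choosing. As an illustration under a further assumption, suppose two classes split a normal score at its median. Then 0.9 per SD of that score implies a between-class HR of about 4.2, and power by formula is about 22% with 8 events and 34% with 11.2. That is better than Step 2 and still far below 90%.

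Neither reply rescues the stated figure, because Step 1 fails for the continuous reading that they favour.

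**Conclusion.** The point holds in two parts. On the plan's inputs, over 90% at alpha 0.005 is not attained even for a continuous predictor: two-sided power is about 40% to 71% for 8 to 14 events, against about 21 events needed. For latent classes the per-SD figure does not apply. A coefficient of 0.9 between two classes has about 2–13% power two-sided by formula, up to about 19% one-sided, and at most 22% two-sided even with 20.6 events. Taking 0.9 per SD of the indicator instead assumes a between-class HR of about 6 to 8, which the plan neither states nor justifies.

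These figures rest on carrying over the 5% and 80%, on unstated sidedness, and on assumed class shares of 10–50%. With so few events, all the approximations are rough.

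Two stronger conclusions are tempting. One is that the stated power is sound for continuous predictors and only the scale is wrong; Step 1 contradicts that. The other is that the plan intends to read a null class result as evidence of no difference. No text says so; the risk is that the stated power invites that reading.

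**What to change.** In section 4.2:
- Replace the over-90% figure with the power that the expected events give for a continuous predictor at alpha 0.005. State the event count, the sidedness and whether controls are included.
- Limit that sentence to continuous measures.
- State separately the power or detectable hazard ratio for a class contrast, with the class shares assumed. For two equal classes and 90% power, the detectable hazard ratio is about 18 with 8 events and about 9 with 14.

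In section 4.1, label MACE-by-class comparisons as exploratory and report them with confidence intervals, so that a null result is not read as evidence of no difference.

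The cost is protocol wording and a less favourable stated figure; no new data are needed. Replacing the class predictor with a continuous or principal-component score is optional and not part of this change. It would trade a class-based answer for a per-SD one, and the synopsis mentions principal components only as a multiplicity correction.
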